4.2.3.1 Biomarker Research

Emerging data suggests that expression of PD-L1 on the tumor may predict for benefit from the MK-3475 and other anti-PD-1. Benefit has also been observed in patients whose tumors don't express PD-L1 but the percentage of such patients who benefit is far less. This difference in efficacy with anti- PD-1 drugs has been observed across tumor types. The rate of PD-L1 expression in SCLC is not well defined. We therefore plan to assess the expression of PD-L1 in tumors of patients enrolled on the trial and correlate the presence of PD-L1 with efficacy end points.

Tumor content in diagnostic biopsies is likely to be limited in SCLC patients. In addition, biopsy of residual tumor following initial chemotherapy may be challenging. Circulating tumor cells (CTCs) hold great promise as a readily available source material that can offer real-time insight into a tumor's genomic architecture. CTCs can be detected in small cell lung cancer patients and appear to have prognostic importance (20, 21). We propose to collect CTCs and assess PD-L1 expression in CTCs an attempt to correlate PD-L1 expression in CTCs with patient's primary tumor and with efficacy parameters.

5.0 ELIGIBILITY

5.1 Inclusion Criteria

1. Patients with extensive stage SCLC who have completed at least 4 cycles of platinum (carboplatin/cisplatin) and etoposide chemotherapy as their first line therapy and have responding or stable disease to this therapy are eligible for this study. Patients who received platinum/etoposide previously for SCLC and it was repeated for recurrence will not be eligible.
2. Patients should be willing and able to provide written informed consent for the trial.
3. Be ≥ 18 years of age on day of signing informed consent.
4. Have a performance status of 0 or 1 on the ECOG Performance Scale.
5. Demonstrate adequate organ function as defined in Table 1, all screening labs should be performed within 14 days of treatment initiation.

Table 1 Adequate Organ Function Laboratory Values

System	Laboratory Value
Hematological	
Absolute neutrophil count (ANC)	≥1,500 /mcL
Platelets	≥100,000 / mcL
Hemoglobin	≥9 g/dL or ≥5.6 mmol/L
Renal	
Serum creatinine OR Measured or calculated ^a creatinine clearance (GFR can also be used in place of creatinine or CrCl)	≤1.5 X upper limit of normal (ULN) OR ≥45 mL/min for subject with creatinine levels > 1.5 X institutional ULN
Hepatic	
Serum total bilirubin	≤ 1.5 X ULN OR Direct bilirubin ≤ ULN for subjects with total bilirubin levels > 1.5 ULN
AST (SGOT) and ALT (SGPT)	≤ 2.5 X ULN OR ≤ 5 X ULN for subjects with liver metastases
^a Creatinine clearance should be calculated per institutional standard.	

6. Female subject of childbearing potential should have a negative urine or serum pregnancy within 1 week prior to receiving the first dose of study medication. If the urine test is positive or cannot be confirmed as negative, a serum pregnancy test will be required.
7. Female subjects of childbearing potential should be willing to use 2 methods of birth control or be surgically sterile, or abstain from heterosexual activity for the course of the study through 120 days after the last dose of study medication (Reference Section 5.7.2). Subjects of childbearing potential are those who have not been surgically sterilized or have not been free from menses for > 1 year.
8. Male subjects should agree to use an adequate method of contraception starting with the first dose of study therapy through 120 days after the last dose of study therapy.

5.2 Exclusion Criteria

The subject must be excluded from participating in the trial if the subject:

1. Is currently participating in or has participated in a study of an investigational agent within 4 weeks of the first dose of treatment.
2. Has a diagnosis of immunodeficiency or is receiving systemic steroid therapy greater than 10 mg/day prednisone equivalent or any other form of immunosuppressive therapy within 7 days prior to the first dose of trial treatment.
3. Has had a prior monoclonal antibody within 4 weeks prior to study Day 1 or who has not recovered (i.e., ≤ Grade 1 or at baseline) from adverse events due to agents administered more than 4 weeks earlier.

4. Has had prior chemotherapy, targeted small molecule therapy, or **definitive** radiation therapy within 2 weeks prior to study Day 1 or who has not recovered (i.e., \leq Grade 1 or at baseline) from adverse events due to a previously administered agent. **Patients who received palliative radiation to any site or prophylactic cranial radiation (\leq 30 Gy) or thoracic RT can start therapy with the study drug 7 days after the last day of radiation therapy as long as they have recovered from any adverse effects (i.e., \leq Grade 1 or at baseline) of such radiation therapy.**
 - Note: Subjects with \leq Grade 2 neuropathy or adverse events that are not considered clinically meaningful such as alopecia are an exception to this criterion and may qualify for the study.
 - Note: If subject received major surgery, they must have recovered adequately from the toxicity and/or complications from the intervention prior to starting therapy.
5. Has a known additional malignancy that is progressing or requires active treatment. Patient will be eligible if other malignancy is controlled and the treating physician determines that the patient's outcome is unlikely to be affected by the other tumor.
6. Has symptomatic central nervous system (CNS) metastases and/or carcinomatous meningitis. Subjects with previously treated brain metastases may participate provided they are **clinically** stable and any neurologic symptoms have returned to baseline, have no **clinical** evidence of new or enlarging brain metastases, and are not using steroids greater than prednisone 10mg/day or equivalent dose of another steroid, prior to start of trial treatment.
7. Has an active autoimmune disease, including a paraneoplastic syndrome of autoimmune nature, requiring systemic treatment other than chemotherapy for SCLC, within the past 3 months or a documented history of clinically severe autoimmune disease, or a syndrome that requires or required systemic steroids or immunosuppressive agents. Subjects with vitiligo or resolved childhood asthma/atopy would be an exception to this rule. Subjects that require intermittent use of bronchodilators or local steroid injections would not be excluded from the study. Subjects with hypothyroidism stable on hormone replacement or Sjorgen's syndrome will not be excluded from the study.
8. Has evidence of active, non-infectious pneumonitis.
9. Has an active infection requiring therapy.
10. Has a history or current evidence of any condition, therapy, or laboratory abnormality that might confound the results of the trial, interfere with the subject's participation for the full duration of the trial, or is not in the best interest of the subject to participate, in the opinion of the treating investigator.

11. Has known psychiatric or substance abuse disorders that would interfere with cooperation with the requirements of the trial.
12. Is pregnant or breastfeeding, or expecting to conceive or father children within the projected duration of the trial, starting with the pre-screening or screening visit through 120 days after the last dose of trial treatment.
13. Has received prior therapy with an anti-PD-1, anti-PD-L1, anti-PD-L2, anti-CD137, or anti-Cytotoxic T-lymphocyte-associated antigen-4 (CTLA-4) antibody (including ipilimumab or any other antibody or drug specifically targeting T-cell co-stimulation or checkpoint pathways).
14. Has a known history of Human Immunodeficiency Virus (HIV) (HIV 1/2 antibodies).
15. Has known active Hepatitis B (e.g., HBsAg reactive) or Hepatitis C (e.g., HCV RNA [qualitative] is detected).
16. Has received a live vaccine within 30 days prior to the first dose of trial treatment.

6.0 TRIAL TREATMENTS/PROCEDURE

All patients deemed eligible and registered with Study Coordinator, the Clinical Trials Office at Karmanos Cancer Institute, will initiate study therapy within 5 days of registration. Please see section 7.0 for all required tests and assessments prior to registration. This is a single arm study so all eligible patients will receive the study treatment MK-3475.

Patients will start therapy no **earlier than 3 weeks** from the first day of the last cycle of platinum/etoposide chemotherapy and **no later than 8 weeks** from the first day of the last cycle of chemotherapy. Due to logistical and administrative issues therapy maybe started within 48 hours before the 3 weeks from the first day of the last cycle of chemotherapy or within 48 hours after 8 weeks of the first day of the last cycle of chemotherapy, **after consultation with the Principal Investigator.**

The treatment to be used in this trial is outlined below in Table 2

Table 2 Trial Treatment

Drug	Dose/Potency	Dose Frequency	Route of Administration
MK-3475	200 mg	Every 3 weeks	IV infusion

Treatment will continue for 24 months unless patient experiences intolerable adverse events or disease progression or patient desires to discontinue therapy.

6.1.1 Dose Modification

6.1.1.1 Dose Modification

There is no dose reduction allowed on the protocol. However the dosing frequency can be increased from 3 weeks to every 4 weeks. MK-3475 will be withheld for drug-related Grade 4 hematologic toxicities, non-hematological toxicity \geq Grade 3 including laboratory abnormalities, and severe or life-threatening AEs as per Table 3 below. **In addition, the drug can be held for any grade of toxicity by the treating physician if it is felt that it is in the best interest of the patient**

Table 3: Dose modification guidelines for drug-related adverse events.

Toxicity	Grade	Hold Treatment (Y/N)	Timing for restarting treatment	Dose/Schedule for restarting treatment	Discontinue Subject (after consultation with Sponsor)
Hematological Toxicity	1, 2, 3*	No	N/A	N/A	N/A
	4	Yes	Toxicity resolves to Grade 0-1 or baseline	May increase the dosing interval by 1 week	Toxicity does not resolve within 12 weeks of last infusion Permanent discontinuation should be considered for any severe or life-threatening event
Non-hematological toxicity	1	No	N/A	N/A	N/A
	2	Consider withholding for persistent symptoms	Toxicity resolves to Grade 0-1 or baseline	Clinical AE resolves within 4 weeks: Same dose and schedule (reference Section 5.6.1.2 for recommendations regarding pneumonitis) Clinical AE does not resolve within 4 weeks: May increase the dosing interval by 1 week	Toxicity does not resolve within 12 weeks of last infusion

Note: Exception to be treated similar to grade 1 toxicity

- Grade 2 alopecia
- Grade 2 fatigue

For additional information regarding Adverse Events with a potential Immune-Etiology reference Section 6.3.1.1

Toxicity	Grade	Hold Treatment (Y/N)	Timing for restarting treatment	Dose/Schedule for restarting treatment	Discontinue Subject (after consultation with Sponsor)
	3, 4	Yes	Toxicity resolves to Grade 0-1 or baseline	May increase the dosing interval by 1 week	Toxicity does not resolve within 12 weeks of last infusion Permanent discontinuation should be considered for any severe or life-threatening event

With investigator and Principal Investigator agreement, subjects with a laboratory adverse event still at Grade 2 after 12 weeks may continue treatment in the trial only if asymptomatic and controlled. **A patient who requires longer than 12 weeks but less than 24 weeks to recover from an adverse event that led to the withholding of the drug could be restarted on the drug IF the treating physician believes that it is in the best interest of the patient to restart the drug and the patient is agreeable. This has to be discussed with the Principal Investigator before restarting the drug.**

Subjects who experience a recurrence of the same severe or life-threatening event at the same grade or greater with re-challenge of MK-3475 should be discontinued from trial treatment.

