6.3.1.1.1a Diarrhea- All attempts should be made to rule out other causes such as metastatic disease, bacterial or parasitic infection, viral gastroenteritis, or the first manifestation of an inflammatory bowel disease by examination for stool leukocytes, stool cultures, and a Clostridium difficile titer.

Course of Action

Grade 1 diarrhea:

- Treat symptomatically (loperamide, oral hydration, electrolyte substitution and ADA colitis diet).
- Endoscopy is recommended if symptoms persist.

Grade 2 diarrhea (or persistent Grade 1):

- Hold MK-3475.
- GI consultation and endoscopy is recommended to confirm or rule out colitis for Grade 2 diarrhea that persists >1 week or Grade 1-2 diarrhea with rectal bleeding (additional guidelines for the treatment of persistent colitis are provided below).

- Grade 1 events that persist for >1 week or Grade 2 events should be treated with the addition of oral diphenoxylate hydrochloride and atropine sulfate four times daily and budesonide 9 mg daily.
- Grade 2 diarrhea with diffuse ulceration and bleeding seen on endoscopy may require oral steroids with prolonged taper and represent an increased risk for the development of bowel perforation.
- When symptoms improve to Grade 1 or less, steroid taper should be started and continued over no less than 4 weeks.

Grade 3-4 diarrhea (or Grade 2 diarrhea that persist after initial steroid treatment):

- Hold/Discontinue MK-3475.
- Rule out bowel perforation. Imaging with plain films or CT can be useful.
- Consider consultation with Gastroenterologist and confirmation biopsy with endoscopy
- Treat with intravenous steroids (methylprednisolone 125 mg) followed by high dose oral steroids (prednisone 1 to 2 mg/kg once per day or dexamethasone 4 mg every 4 hours) When symptoms improve to Grade 1 or less, steroid taper should be started and continued over no less than 4 weeks. Taper over 6 to 8 weeks in patients with diffuse and severe ulceration and/or bleeding.

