3.1 Colitis

The following AE terms, if considered \geq Grade 2, are considered ECIs and should be reported to the Principal Investigator within 72 hours of the event:

- Bowel obstruction
- Colitis
- Colitis microscopic
- Enterocolitis
- Enterocolitis hemorrhagic
- GI perforation
- Necrotizing colitis

Diarrhea should be reported as an ECI if it is \geq Grade 3.

The following signs and symptoms may be associated with any of the above diagnosis. The signs and symptoms below may represent one of the included adverse events, but do not need to be reported as an ECI unless the investigator suspects one of the ECI events listed above.

Symptoms

Symptoms may include (but not limited to):

- Abdominal pain, cramping and/or bloating
- Blood and/or mucus in stool with or without fever
- Constipation
- Diarrhea

- Ileus
- Nausea and/or vomiting
- Peritoneal signs consistent with bowel perforation
- Rectal bleeding
- With or without fever

Differential Diagnosis

All attempts should be made to rule out other causes such as metastatic disease, bacterial or parasitic infection, viral gastroenteritis, or the first manifestation of an inflammatory bowel disease by examination for stool leukocytes, stool cultures, and a *Clostridium difficile* titer.

Course of Action

Grade 1 diarrhea:

- Treat symptomatically (loperamide, oral hydration, electrolyte substitution and ADA colitis diet).
- Endoscopy is recommended if symptoms persist.

Grade 2 diarrhea (or persistent Grade 1):

- Hold MK-3475.
- GI consultation and endoscopy is recommended to confirm or rule out colitis for Grade 2 diarrhea that persists >1 week or Grade 1-2 diarrhea with rectal bleeding (additional guidelines for the treatment of persistent colitis are provided below).
- Grade 1 events that persist for >1 week or Grade 2 events should be treated with the addition of oral diphenoxylate hydrochloride and atropine sulfate four times daily and budesonide 9 mg daily.
- Grade 2 diarrhea with diffuse ulceration and bleeding seen on endoscopy may require oral steroids with prolonged taper and represent an increased risk for the development of bowel perforation.
- When symptoms improve to Grade 1 or less, steroid taper should be started and continued over no less than 4 weeks.

Grade 3-4 diarrhea (or Grade 2 diarrhea that persist after initial steroid treatment):

- Hold/Discontinue MK-3475.
- Rule out bowel perforation. Imaging with plain films or CT can be useful.

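### Table 3 gives a weaker hold instruction than the event-specific text for low-grade diarrhoea, Grade 2 enterocolitis and Grade 2 pneumonitis, and nothing says which governs

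*Combined protocol and SAP*

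**What the plan says.** Table 3 in Section 6.1.1.1 is titled "Dose modification guidelines for drug-related adverse events". In its non-haematological rows the hold column reads No at Grade 1 and "Consider withholding for persistent symptoms" at Grade 2. The paragraph above the table requires withholding only from non-haematological Grade 3 upward, then adds that "the drug can be held for any grade of toxicity by the treating physician" if that serves the patient's interest. The table names two Grade 2 exceptions, alopecia and fatigue, to be handled as Grade 1.

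The event-specific text says something different:

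- Section 6.3.1.1.1a, under the heading "Grade 2 diarrhea (or persistent Grade 1"), gives holding MK-3475 as its first action. Appendix 15.4 section 3.1 repeats this.
- Section 6.3.1 says the drug should be withheld for Grade 2 enterocolitis.
- Table 6 in Section 6.3.1.1.1g says to withhold for Grade 2 pneumonitis, and Appendix 15.4 section 3.5 also says to hold.

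Two pointers lead from Table 3 to this material. One is a note: "For additional information regarding Adverse Events with a potential Immune-Etiology reference Section 6.3.1.1". The other sits in the Grade 2 restart column: "reference Section 5.6.1.2 for recommendations regarding pneumonitis".

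**The concern.** Two sites could treat the same patient differently and each point to protocol text. One that opens Table 3 sees No, or a suggestion limited to persistent symptoms, and may give the next infusion. One that opens the diarrhoea, enterocolitis or pneumonitis section sees an instruction to hold.

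Table 3 is the less cautious text for events where continued dosing could matter: Section 6.3.1.1.1a warns that Grade 2 diarrhoea with diffuse ulceration and bleeding on endoscopy carries a raised risk of bowel perforation. The study also plans 4-5 sites (Section 11.2) with remote monitoring (Section 13.5), and a monitor could not say from the protocol whether dosing on was a deviation.

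**Working it through.** No formula applies. The check sets the instructions side by side, looks for a ranking rule, and then asks which other provisions would catch the patient.

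**Step 1. The instructions compared.**

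| Situation | Table 3 | Event-specific text |
|---|---|---|
| Persistent Grade 1 diarrhoea | No | Hold (6.3.1.1.1a; 15.4 section 3.1) |
| Grade 2 diarrhoea | Consider, if symptoms persist | Hold (same sections) |
| Grade 2 enterocolitis | Consider, if symptoms persist | Should be withheld (6.3.1) |
| Grade 2 pneumonitis | Consider, if symptoms persist | Withhold (Table 6); hold (15.4 section 3.5) |

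All four pairs differ: 1 direct contradiction + 3 conditional suggestions against a directed hold = 4. None of the three Grade 2 holds depends on persistence.

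**Step 2. Is there a ranking rule?**

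- The Table 3 note offers 6.3.1.1 as further information, with no override wording. The Grade 2 enterocolitis rule is in 6.3.1, outside that pointer.
- The pneumonitis pointer concerns restarting, and there is no Section 5.6.1.2; pneumonitis is at 6.3.1.1.1g.
- For continuing treatment after Grade 2 enterocolitis, 6.3.1 refers to Section 5.2, which is now the exclusion criteria. Section 6.1.2 refers to a Section 5.2.1.2 that does not exist.
- Section 15.4 section 3.5 tells the reader to hold as the protocol specifies, which leads back to a main text where Tables 3 and 6 differ.
- Table 5 is expressly limited to immune-related events not covered elsewhere. Table 3 carries no such limit, and its listed exceptions omit these events.

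No sentence ranks Table 3 against the event-specific sections.

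**Step 3. What else would catch the patient?**

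- Grade 2 colitis, enterocolitis and pneumonitis are events of clinical interest (ECIs), reportable to the Principal Investigator within 72 hours regardless of attribution (15.4 section 2 and Table 10).
- Section 6.3.1.1.1g says patients with symptomatic pneumonitis should stop the drug at once.
- Section 6.3.1.1 says immune-related events of Grade 2 or higher should be discussed immediately with the Principal Investigator.
- Section 6.3.1.1.1 calls for Principal Investigator contact within 72 hours for each condition it lists, once other causes are judged less likely. Diarrhoea is the first listed, with no grade threshold.
- The formal ECI trigger for diarrhoea is narrower. Section 3.1 of 15.4 sets it at Grade 3 ("Diarrhea should be reported as an ECI if it is" at or above that grade), and Table 10 adds any grade that leads to dose modification. Signs and symptoms, diarrhoea among them, "do not need to be reported as an ECI unless the investigator suspects one of the ECI events listed above". Reading a hold as a dose modification, a site that doses on below Grade 3 does not set off this trigger unless it suspects a listed event such as colitis.

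These provisions bring the case to attention. None says whether the next dose should be given.

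**Step 4. Frequency.** Section 4.2.1 lists diarrhoea among common adverse events, and puts colitis and pneumonitis considered immune-related each below 5% of phase I patients. It gives no rate for Grade 1-2 diarrhoea and no Grade 2 rate for the other two, so no expected number of affected patients can be given.

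**The case against.** The strongest reply is that Table 3 is generic, the later sections are specific, and specific text is ordinarily read as controlling. Considering a hold does not forbid one, the physician may hold at any grade, and the table sends readers to the immune-event section. A site that holds therefore breaches nothing. Pneumonitis is singled out within the table and, despite the stale number, has a section of its own title. Harm requires a site to read Table 3 in isolation.

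Much of this stands, and it limits the weight of the point. But the precedence is inferred, not written, and permission to hold protects only the physician who already intends to. It does not tell a reader of No that a hold is directed elsewhere. Soft framing as guidance applies to both sets of text, so it does not rank them.

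Three stronger readings are tempting and are not supported:

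- *That low-grade diarrhoea can pass without the Principal Investigator hearing of it.* Section 6.3.1.1.1 calls for contact within 72 hours at any grade, though only after work-up points away from other causes. Only the formal ECI trigger depends on dose modification.
- *That a 72-hour report would normally arrive before the next three-weekly infusion.* The clock starts when the investigator becomes aware (15.4), and the flow chart places adverse event review at treatment visits, so an event may first be found on a dosing day. Reporting is also not holding.
- *That the efficacy result is compromised.* Nothing here changes the definition or analysis of progression-free survival.

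**Conclusion.** The point holds as a conflict between written instructions, with Table 3 the less safe of the two. Its size is four situations: one outright contradiction (persistent Grade 1 diarrhoea) and three where a conditional suggestion meets a directed hold (Grade 2 diarrhoea, enterocolitis and pneumonitis). Practical exposure is smaller for enterocolitis and pneumonitis, where early reporting applies whatever the attribution. It is larger for diarrhoea, where contact with the Principal Investigator follows a judgement about cause.

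The conclusion rests on the text alone and assumes that some site staff will dose from Table 3 without opening the event sections. How often that would happen is unknown. The correction should be made for patient safety and consistent conduct across sites; it is not a flaw that undermines the trial.

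**What to change.** Add to the note under Table 3:

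> *Exceptions: hold MK-3475 for Grade 2 or persistent Grade 1 diarrhea, Grade 2 enterocolitis/colitis and Grade 2 pneumonitis (Sections 6.3.1, 6.3.1.1.1a, 6.3.1.1.1g). Where this table and an event-specific section differ on holding, the stricter instruction applies.*

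Do not write a blanket rule that the event-specific section always overrides the table. For Grade 2 hepatic events, Section 6.3.1.1.1d lists only more frequent liver function monitoring, so such a rule would remove Table 3's prompt to consider withholding.

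As housekeeping, change 5.6.1.2 in Table 3 to 6.3.1.1.1g, and change both 5.2 in Section 6.3.1 and 5.2.1.2 in Section 6.1.2 to 6.1.1.1.

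The cost is protocol wording: two sentences and three section numbers. There are no new procedures, and the sample size and analysis do not change.
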